1.3.4.1 Adverse Reactions Leading to Treatment Discontinuation

Of the 398 Xyrem-treated patients with narcolepsy, 10.3% of patients discontinued because of adverse reactions compared with 2.8% of patients receiving placebo. The most common adverse reaction leading to discontinuation was nausea (2.8%). The majority of adverse reactions leading to discontinuation began during the first few weeks of treatment.

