### 7.2. MISSING DATA

Missing or partially missing concomitant medications and AEs start and stop dates will be imputed as described in [APPENDIX 2](#). However, imputed dates will NOT be presented in the listings as their sole

purpose will be for the classification of the medications as past, concomitant or post (refer to [section 9.5](#)) and the classification of the AEs as prior, treatment-emergent or post (refer to [section 9.9.1](#)).

Missing cataplexy attacks data will be handled as described in [sections 9.8.1.3](#) and [9.8.1.5](#).

Missing questionnaire data will be handled as described in the following sections:

- ESS:
  - Individual item scores: [section 9.8.2.1](#)
  - Total score: [section 9.8.2.2](#)
- PGIC and CGIc: [section 9.8.3.2.1](#)
- CGIs: [section 9.8.4.1](#)
- SF-36:
  - Scales and overall components: [section 9.8.3.2.2](#)
- EQ-5D-5L:
  - Dimensions: [section 9.8.3.1.4](#)
  - Crosswalk index score: [section 9.8.3.3.3](#)
- PHQ-9: [section 9.9.5.2](#)

Missing safety data (other than PHQ-9) will not be imputed.

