### 9.9.1. ADVERSE EVENTS

AEs will be coded to SOC and PT using the MedDRA dictionary, version 19.1 and will be classified as follows:

- **Prior AEs** are defined as AEs that started on or after the signature of the Main Study informed consent but prior to the first dose of OL OTTP study drug;
- **For the overall summaries**, (TEAEs) are defined as any AEs that started or worsened in severity on or after the first dose of Open-Label study drug up to the last dose of study drug during the Open-Label Optimized Treatment and Titration period, Open-Label Stable-Dose Period, Double-Blind Randomized-Withdrawal Period or Open-Label Extension period (whichever is the latest) + 30 days.
- **For the DB RWP**, TEAEs are defined as any AEs that started or worsened in severity on or after the first dose of double-blind study drug up to 1) the last dose of double-blind study drug for subjects who did not enter the Open-Label Extension, 2) the first dose of study drug during the Open-Label Extension for subjects who rolled over into the Open-Label Extension immediately

after having completed the Main Study or 3) whichever occur first between the following two timepoints for subjects who rolled over into the Open-Label Extension after having re-entered into the study: last dose of double-blind study drug or first dose of study drug during the Open-Label Extension.

- **For the Main Study**, TEAEs are defined as any AEs that started or worsened in severity on or after the first dose of study drug up to the first day of the Open-Label Extension period for rollover subjects; or the first day of the Open-Label Extension period or the day of the last dose of study drug in the Double-Blind Randomized-Withdrawal period + 30 days (whichever is the earliest) for re-entry subjects.
- **For the OLE**, TEAEs are defined as any AEs that started or worsened in severity on or after the first dose of Open-Label study drug during the Open-Label Extension period up to the last dose of study drug + 30 days.
- **Post AEs** are defined as any AEs that started or worsened in severity after the last dose of study drug during the OTTP, SBP, RWP or OLE (whichever is the latest) + 30 days.

For OLE re-entry subjects, AEs occurring after their last dose of DB study drug, but prior to their first dose of OLE study drug will be considered as post AEs .

Only TEAEs will be summarized, but all AEs will be presented in the subject data listings.

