#### **9.9.1.5. SERIOUS ADVERSE EVENTS**

A listing including all SAEs will be provided.

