**ALGORITHM FOR TREATMENT EMERGENCE OF ADVERSE EVENTS**

START DATE	STOP DATE	ACTION
Known	Known, Partial, Missing	
 
• If AE start date or worsened in severity < study drug first dose date, then not TEAE
 
• If study drug first dose date ≤ AE start date or worsened in severity ≤ (study drug last dose date + 30 days), then TEAE
 

Partial, but known components show that it cannot be on or after study drug first dose date	Known, Partial, Missing	Not TEAE
Partial, but known components show that it could be on or after study first dose date	Known	
 
• If AE stop date < study drug first dose date, then not TEAE
 
• If study drug first dose date ≤ AE worsened in severity or stop date ≤ (study drug last dose date + 30 days), then TEAE
 

or	Partial	If known components show that: 
 
• AE stop date < study drug first dose date, then not TEAE
 
• {[Study drug first dose date ≤ AE stop date ≤ (study drug last dose date + 30 days)] or [(study drug last dose date + 30 days) < AE stop date]}, then TEAE
 

Missing	Missing	Assumed TEAE

Note: Missing days will be assumed to be the first day of the month and missing months will be assumed to be the first month of the year for the purposes of determining if a partial date could be on or after the study first dose date (i.e. first day of month if day unknown or 1st January if day and month are unknown),.

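### The SAP's note on partial AE start dates contradicts its own table and, read literally, makes AEs dated only to the first-dose month or year not treatment-emergent

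*SAP*

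**What the plan says.** SAP section 7.2 sends missing or partial AE dates to Appendix 2 and states that the imputed dates serve "the classification of the AEs as prior, treatment-emergent or post". SAP section 9.9.1 then gives that classification its weight: "Only TEAEs will be summarized, but all AEs will be presented in the subject data listings".

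The Appendix 2 algorithm for treatment emergence has two rows for a partial start date:

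- "Partial, but known components show that it cannot be on or after study drug first dose date": the event is not a TEAE, whatever is known of the stop date.
- "Partial, but known components show that it could be on or after study first dose date": the stop date decides. A stop before first dose gives not TEAE; a later stop gives TEAE (for a fully known stop, up to 30 days after last dose). If the stop is missing, the event is assumed to be a TEAE. A completely missing start date is handled in this row as well.

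The note under the table reads "Missing days will be assumed to be the first day of the month and missing months will be assumed to be the first month" (that is, January), and gives its use as "for the purposes of determining if a partial date could be on or after the study first dose date".

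**The concern.** The rows ask whether a start on or after first dose is possible. The note answers by testing the earliest date the event could have started. If that date is on or after first dose, the event certainly started on or after first dose. The note therefore replaces a test of possibility with a test of certainty, and the two give different answers in the month and year of first dose.

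The ordering that results is perverse. An event with no start or stop date is assumed treatment-emergent, while one known to have begun in the first-dose month is normally excluded. More information makes the event less likely to be counted. Setting a start to the earliest date is cautious for medications, where it favours calling a drug concomitant. For AEs it works the other way.

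At stake are the TEAE incidence, severity, relatedness, discontinuation and special-interest summaries, and the discontinuation and special-interest listings, which are restricted to TEAEs. The affected window is the start of dosing. Protocol section 1.3.4.1 says of earlier Xyrem trials: "The majority of adverse reactions leading to discontinuation began during the first few weeks of treatment". AEs are collected from consent (Protocol section 6.13.6), so the boundary between pre-dose and post-dose events is in real use.

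**Working it through.** The plan states no figure here, so the check is to apply both rules to the same dates.

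**Inputs.** The two rows and the note in SAP Appendix 2. Assumed: a 365-day year, every date taken in turn as the first-dose date, and an AE start known only to the month, or only to the year, of first dose.

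**Where the rules can differ.** A start in a month wholly before the first-dose month is not a TEAE under either rule. A start in a later month passes the start-date test under both. The conflict is confined to the first-dose month (month-only dates) and the first-dose year (year-only dates).

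**Note, read literally.** The start passes only if the imputed date is on or after first dose.

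- Month-only: the 1st of the month is on or after first dose only when first dose is itself on the 1st. There are 12 such dates, so the event is excluded on 365 − 12 = 353 dates; 353/365 = 96.7%.
- Year-only: 1 January is on or after first dose only when first dose is on 1 January. Excluded on 365 − 1 = 364 dates; 364/365 = 99.7%.

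**Row wording.** The latest date compatible with the known parts is the last day of the month, or 31 December. Neither can precede a first dose in the same month or year. Excluded on the start date: 0/365 in both cases.

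**Example (invented dates).** First dose 10 March 2017, AE start March 2017, stop 20 May 2017. Note: start set to 1 March, before first dose, so not a TEAE and the stop date is never consulted. Rows: a start on 10 March or later is possible and the stop is after first dose, so TEAE.

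**Internal check.** Under the note, a partial start reaches the second row only if its earliest possible date is on or after first dose. Such an event cannot have stopped before first dose. The row's outcome for a stop before first dose can then never be reached for a partial start, which suggests the rows were not written with this test in mind.

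**How many excluded events would be true TEAEs?** The documents cannot say. As an illustration only, take a 30-day month with dosing day and onset both uniform. A first dose on day d leaves (31 − d)/30 of the month on or after dosing. Averaged over d = 1 to 30 this is 465/900 = 51.7%. About half would be true TEAEs and half true pre-dose events. Onset clustered after dosing would raise the share; onset clustered in screening would lower it.

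**The case against.** The strongest reply is that the outcome is not settled. Nothing ranks the note above the rows, and an imputed 1st of the month or January is not a known component of the date. A programmer following the rows would class the March example as a TEAE. This stands: the defect is a contradiction, and exclusion follows only if the note is followed literally.

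Exposure is also likely to be small. AEs are recorded at every contact, weekly through the 12-week titration period (Protocol section 7.1.2.3 and the schedule of events), so a start known only to the year is barely plausible. A change in severity is entered as a new AE (Protocol section 6.13.2), so a worsening gets its own start date. The first-dose month is open-label and single-arm, and Groups 1 and 2 enter on stable Xyrem, so the early-onset pattern carries over to them less directly. All of this limits the size but does not remove the contradiction.

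Three stronger readings are tempting and are not supported:

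- **That these AEs vanish from all safety reporting.** They stay in the subject listings. For serious events, "A listing including all SAEs will be provided", and AEs with an outcome of death are listed too. Laboratory, ECG, vital-sign, C-SSRS and PHQ-9 outputs do not use TEAE status.
- **That about 97% of these AEs are misclassified.** The 96.7% is a share of first-dose dates. Screening can run up to 30 days before Day 1, so some events dated to the first-dose month did begin before dosing and are rightly excluded.
- **That the comparison of arms in the double-blind period is distorted.** The note refers only to the study first-dose date. The SAP does not say that it governs period-specific TEAEs.

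**Conclusion.** The concern holds as a contradiction within SAP Appendix 2, with one of the two readings wrong in substance. Under the literal note, an AE dated only to the first-dose month is excluded unless dosing began on the 1st (353 of 365 dates), and one dated only to the first-dose year unless dosing began on 1 January (364 of 365). Under the rows, neither is excluded on its start date. These counts assume a 365-day year and nothing else.

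The direction of the error is known: too few events in TEAE summaries and TEAE-restricted listings. Its size is not, because the documents do not give the number of partially dated AEs; frequent contacts suggest few. It has no bearing on the efficacy analyses. It merits correction because the rule as written can give a wrong result and is cheap to repair.

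**What to change.** Replace the note with: A partial start date is treated as possibly on or after the first dose unless its latest possible date (last day of the known month, or 31 December of the known year) is before the first dose; the stop-date rules in the table then apply.

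Apply this to study-level TEAEs. If the SAP also means it for period-specific TEAEs, it needs a further rule that assigns an event to one period only. The double-blind period lasts 2 weeks, so for a rollover subject its first dose and the first open-label extension dose can fall in the same calendar month. A month-only event could then be counted in both.

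The cost is one sentence in Appendix 2 and one programming rule. The downside is that TEAE counts may rise slightly because some events that began before dosing will be included, which for a safety summary is the cautious direction.

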## APPENDIX 3. LIST OF STIMULANT MEDICATIONS

The following standardized WHO dictionary medication names are considered stimulant medications:

METHAMPHETAMINE  
AMPHETAMINE  
DEXTROAMPHETAMINE  
METHAMPHETAMINE SULFATE  
LISDEXAMFETAMINE MESILATE  
ARMODAFINIL  
METHYLPHENIDATE  
METHYLPHENIDATE HYDROCHLORIDE  
MODAFINIL  
DEXMETHYLPHENIDATE  
MAZINDOL

## APPENDIX 4. EQ-5D-5L CROSSWALK VALUE SETS

EQ-5D-5L\_Crosswalk\_Value\_Sets.xls

## APPENDIX 5. LIST OF CLINICAL LABORATORY TESTS

### Hematology

- Complete blood count (CBC), including platelet count and white blood cell (WBC) with differential

### Urinalysis

- Appearance
- Bilirubin
- Color
- Glucose
- Ketones
- Nitrite
- Occult blood
- pH
- Protein
- Specific gravity
- Urobilinogen

### Pregnancy Screen\*

- Serum at screening
- Urine at start of OL Optimized Treatment and Titration Period

### Drug Screen (urine)

### Alcohol Screen

### Serum Chemistry

- Albumin
- Alkaline phosphatase (ALK-P)
- ALT
- AST
- Blood urea nitrogen (BUN)
- Calcium
- Chloride
- Creatinine
- Creatine kinase
- Gamma-glutamyl transferase (GGT)
- Globulin
- Glucose
- Lactate dehydrogenase (LDH)
- Phosphorus
- Potassium
- Sodium
- Magnesium
- Total bilirubin
- Direct bilirubin
- Total cholesterol
- Total protein
- Triglycerides
- Uric acid
- TSH (screening only)

\* Pregnancy screening is required for all females of childbearing potential. Female subjects who have undergone surgical sterilization, who are post-menopausal (defined as >1 year of amenorrhea), who have medically documented ovarian failure (defined as serum estradiol and follicle-stimulating hormone [FSH] levels within the institutional postmenopausal range and a negative serum or urine • HCG) do not need to undergo pregnancy screening.
